5 METHODOLOGY FOR STATISTICAL ANALYSIS

5.1 NUMBER OF SUBJECTS NEEDED (NSN)

The objective of a non-inferiority study is to demonstrate that the mean difference between the 2 devices remains small and clinically insignificant.

The average blood glucose level achieved in real life with the Omnipod pump corresponds to an estimated average HbA1c of 7.8% based on the experience of the three centers in the study's scientific committee, which is consistent with the literature. We can assume that the average blood glucose level on the Medtrum pump is the same as on the Omnipod pump. Setting the Δ threshold for non-inferiority at +0.4%, in accordance with FDA guidance (Guidance for Industry Diabetes Mellitus (Developing Drugs and Therapeutic Biologics for Treatment and Prevention)), if the upper threshold of the IC95% difference between the 2 pumps (Medtrum-Omnipod) exceeds Δ (i.e., 0.4), non-inferiority will not be demonstrated. Otherwise, the superiority of the Medtrum pump over the Omnipod pump can be tested, with a Δ ' threshold set at -0.3%.

On the basis of these assumptions, based on the so-called "Less is better" design with $\alpha = 2.5\%$, $\beta = 20\%$, and a standard deviation (SD) set at 0.55, the calculation of the necessary number of (analyzable) subjects was 60 patients (30 in each group).

Assuming that 20% of patients could not be analyzed (major discrepancies, missing data, lost to follow-up), the number of patients to be randomized was 75.

100 patients were finally included; to confirm our standard deviation hypothesis, a descriptive analysis of baseline HbA1c data for the entire population was performed in a blinded fashion at the end of the inclusion period. The standard deviation of the HbA1c estimate (FSL) was equal to 0.8.

With regard to the other assumptions of the protocol:

- Risk of first kind: 2.5%.
- Statistical power: 80%.
- Non-inferiority limit Δ : +0.4
- Assumed value of the difference between the two pumps: 0

The sample of patients needed for the study is estimated at 63 patients per group, for a total of **126 analyzable patients**.

As the study cannot include more than 100 patients, the statistical power of the study will be less than 80%.

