Statistical analysis	
Data processing and statistical analysis will be carried out by the service provider, Axonal-Biostatem.
 
The statistical analyses will be described in a Statistical Analysis Plan (SAP) validated by the Sponsor and the Scientific Committee, prior to the freeze-in.
 
Statistical analyses will be performed after baseline freezing of the data with SAS® software (SAS Institute, NC, Cary, USA), version 9.4 or later.
 
Demographic and efficacy/performance analyses will be performed in the ITT population. The primary endpoint will be analyzed in PP (Per Protocol) and then validated in the ITT (intention to treat) population. The safety analyses will be performed in the safety population.
 
For quantitative variables, the usual statistics (n, missing n, mean, standard deviation (SD), median, first and third quartiles (Q1 and Q3), minimum and maximum) will be presented. IC95% may be

	
presented if relevant (especially for the primary endpoint).
 
For categorical variables, the usual statistics (n, missing n, frequency and percentage) for each modality will be provided.
 
Descriptive statistics will be provided in aggregate and by pump group.
 
The type 1 error, α, is set at 5% when the tests used will be two-sided (superiority) and α will be set at 2.5% when the tests will be one-sided in the case of Noninferiority (IC95%).
 
Analysis of the main objective
 
The non-inferiority analysis will be produced via an Ancova or mixed model on the Per-Protocol population and then on an intention-to-treat basis.
 
If non-inferiority is demonstrated, a superiority analysis will be conducted.
 
Analysis of secondary objectives
 
The secondary criteria will be described and then be the subject of mixed or Ancova models.
 
A non-inferiority analysis on HbA1c data and superiority analyses on Time in range, number of glycemic events, patient satisfaction will be performed.

Regulatory framework	ID-RCB number, CPP opinion, CNIL MR001 and RGPD compliance, information to the ANSM, approval of investigator contracts by the CNOM, transparency obligations
Logistics	CRO Axonal-Biostatem (Nanterre, France)

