11.2.4 Analysis of the effectiveness / performance of the device

Analysis of primary efficacy endpoint:

The non-inferiority analysis of the primary efficacy endpoint will be performed with an ANOVA, with the DM as an explanatory variable, on the *per protocol* population and then on the *intention-to-treat* population. If the upper bound of the IC95% of the Omnipod-Medtrum estimated difference in means (LSmeans) exceeds the non-inferiority bound, it will be rejected.

Non-inferiority bounds are defined in this protocol and will be used in the statistical analysis plan.

If non-inferiority is demonstrated, a superiority analysis will be conducted.

Secondary efficacy endpoint analyses:

The secondary efficacy endpoints will be analyzed for the variables listed below.

Each variable will be described globally and by pump group.

In case of non-inferiority analysis, the same methodology as for the primary endpoint will be used.

In case of comparison of quantitative variables, parametric (T-test) or non-parametric (Mann-Whitney) tests of comparison of means will be used. In case of comparison of qualitative variables, CHI² or Fisher exact tests will be used.

In case of tests on changes within each group, paired data tests will be used (paired data T-test or Wilcoxon signed ranks test, depending on the distribution of the data).

❖ **HbA1c:**

- Evolution of the value measured in the laboratory from a blood sample taken before the D0 visit and just before the 3-month visit
- Description in the total population, in each group and comparison between groups.

❖ **Glucose measurements**

- Average of glucose measurements over each period and over the entire study duration
- Description of the minimum and maximum values over the total duration of the study
- Description of the % of Time in Range (see ADA and International Consensus on Time in Range recommendations^{25,26})
- Description in the total population, in each group and comparison between groups.

❖ **Glycemic events**

- Description of the number of symptomatic and non-symptomatic hypoglycemic events during the evaluation period, broken down by severity level (see ADA consensus definitions²⁵)
- Description of the number of symptomatic and non-symptomatic hyperglycemia events during the evaluation period, broken down by severity level (see ADA consensus definitions²⁵)
- Description in the total population, in each group and comparison between groups.
-

❖ **Device tolerance**

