6 MODIFICATIONS TO THE ANALYSES PROVIDED FOR IN THE PROTOCOL

Not applicable

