7.1.3 Populations of analysis

Analysis populations will be presented with the number of patients in each treatment group. Intent-to-treat (ITT) population: all included and randomized patients who used the pump device at least once.

Intent-to-treat (ITTm) population: ITT population with exclusion of the 4 patients discharged due to COVID-19.

Population Per Protocol (PP): ITT patients with no major protocol deviations.

Tolerance population: all patients who have used the pump device at least once.

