7.4 ANALYSIS OF THE EVALUATION CRITERIA

7.4.1 Primary endpoint analysis

The primary endpoint is the estimate of HbA1c at 3 months based on the mean of continuous glucose measurements obtained during the last 10 weeks of follow-up.

HbA1c estimation will be described by treatment group and then by type of diabetes.

The non-inferiority analysis of the primary efficacy endpoint will be performed with an ANCOVA, with the medical device as an explanatory variable and an adjustment on the estimate of HbA1c at Baseline, on the PP population.

If the upper bound of the IC95% of the Omnipod-Medtrum estimated difference in means (LSmeans) exceeds the non-inferiority bound set at 0.4, non-inferiority will not be demonstrated.

If non-inferiority is demonstrated, a superiority analysis will be conducted. If the upper bound of the IC95% of the estimated difference in mean is less than -0.3, superiority will be demonstrated.

The MIXED procedure (SAS® 9.4) will be used.

Code:

```
proc mixed data=XX order=data;
where PP = 1;
class DM;
model ESTIM_HBA1c = ESTIM_HBA1c_BASELINE DM;
lsmeans DM / diff=control cl;
run;
```

A sensitivity analysis will be performed on the ITTm population with imputation of missing data by the mean or median according to the distribution of the primary endpoint.

A subgroup analysis will be performed on the population of patients with an LSP wear rate >70% at M3.

Exploratory analysis:

Univariate analyses will be conducted on age in 2 classes (below or above the median), sex, type of diabetes, center, and duration of diabetes in 3 classes (<5 years; between 5 and 10 years; >10 years). If the p-value <0.05, the variable will be included in the full model. Then a top-down stepwise strategy will be conducted to select the variables for the final model.

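### Does SAP 5.1 need a power figure for the baseline-adjusted analysis, given that it only says power will fall below 80%?

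*SAP*

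**What the plan says.** Protocol 11.1 plans 60 analysable patients (75 randomised) from a standard deviation (SD) of 0.55, a margin of 0.4, no true difference, a one-sided 2.5% error rate and 80% power. It provides for a blinded check of the baseline SD and, if that differs greatly, a recalculation to keep 80% power.

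SAP 5.1 reports the check: "The standard deviation of the HbA1c estimate (FSL) was equal to 0.8". With the other inputs unchanged it obtains 63 per group, 126 analysable. One hundred patients had been included, and it concludes: "As the study cannot include more than 100 patients, the statistical power of the study will be less than 80" per cent. The loss allowance that took 60 to 75 is restated ("Assuming that 20% of patients could not be analyzed (major discrepancies, missing data, lost to follow-up") but is not applied to the 126 or to the 100.

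The analysis model is described in three places:
- Protocol 11.2.4: the primary analysis "will be performed with an ANOVA, with the DM as an explanatory variable".
- Protocol summary, statistical analysis: "The non-inferiority analysis will be produced via an Ancova or mixed model on the Per-Protocol population".
- SAP 7.4.1: an ANCOVA "with the medical device as an explanatory variable and an adjustment on the estimate of HbA1c at Baseline", on the per-protocol population.

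SAP section 6 records no modification to the protocol's analyses. SAP 7.1.3 defines a modified intention-to-treat set, the "ITT population with exclusion of the 4 patients discharged due to COVID-19".

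**The concern.** The sample-size section and the analysis section seem to describe different analyses. The 0.8 in SAP 5.1 is the raw spread of baseline values, and the formula that returns 63 per group uses it as it stands. An ANCOVA works with the residual spread, which is smaller when baseline and follow-up are correlated. The statement that power is below 80% might therefore not apply to the analysis that will be run.

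The protocol also intended to recalculate so as to keep 80% power. The SAP recalculates and then stops at 100 without giving the reason for that limit or the power that remains. Below 80% could mean 79% or 60%.

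What would be at stake is how an inconclusive result is read. If the interval crosses 0.4, a reader would want to know whether that was likely even with equivalent pumps. On unadjusted inputs with 80 analysable, the chance of missing non-inferiority with truly equal pumps is about 39%, against the planned 20%.

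**Working it through.** **Inputs from the documents.** Margin 0.4; true difference 0; one-sided error 2.5% (z = 1.960); power 80% (z = 0.8416); allocation 1:1; SD 0.55 as first planned and 0.8 at the blinded check; 100 included; 4 COVID-19 discharges; 20% loss allowance.

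**Inputs not in the documents.** The correlation r between baseline and 3-month estimated HbA1c, the SD at 3 months, and the per-protocol count.

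**1. The plan's own figures.** n per group = 2 × (1.960 + 0.8416)² × SD² / 0.4².
- SD 0.55: 29.7, so 30 per group and 60 in all; 60 / 0.8 = 75.
- SD 0.8: 62.8, so 63 per group and 126 in all.

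Both reproduce. A noncentral-t calculation gives 64 per group, a trivial difference.

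**2. Unadjusted power at the available numbers.** Power = Φ(0.4 / (SD × √(2/n)) − 1.960), with SD = 0.8 taken to hold at 3 months.

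| Analysable | n per group | Standard error | Power (normal) | Power (t) |
|---|---|---|---|---|
| 100 | 50 | 0.160 | 70.5% | 69.7% |
| 96 (100 less 4) | 48 | 0.163 | 68.8% | 67.9% |
| 80 (100 less 20%) | 40 | 0.179 | 60.9% | 59.8% |

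Every row is below 80%, as SAP 5.1 says, and every row comes from inputs printed there. The 80 is an extrapolation: the SAP applies its 20% only to go from 60 to 75.

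**3. The planned ANCOVA.** Residual SD = SD × √(1 − r²), put into the same power formula with 40 per group. Both r and the follow-up SD are assumptions.

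| Follow-up SD | r = 0.4 | r = 0.6 | r = 0.8 |
|---|---|---|---|
| 0.7 | 79.6% | 89.1% | 98.9% |
| 0.8 | 68.4% | 79.8% | 96.1% |
| 0.9 | 58.3% | 70.0% | 91.2% |

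The residual SD that gives 80% power with 40 per group is 0.4 / (√(2/40) × 2.8016) = 0.6385. The break-even r is √(1 − (0.6385/SD)²): 0.41, 0.60 and 0.70 for SD 0.7, 0.8 and 0.9. With 100 analysable and SD 0.8, the break-even is about 0.45. Nothing in the documents places r or the follow-up SD on either side of these values.

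**4. Expected precision.** The planned SAS mixed-model procedure uses t limits. With 80 analysable and SD 0.8, the 95% half-width is 1.991 × 0.179 = 0.356 unadjusted, so an observed difference up to about 0.04 would pass (0.4 − 0.356). With r = 0.6 assumed, the half-width is 0.285 and about 0.11 would pass. The trial's own interval will show which of these is closer.

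**The case for a change.** The strongest case for a change is that SAP 5.1 discloses the direction of the shortfall but not its size, the number it applies to, or the model it assumes. Planning precision fixed before outcomes are seen is more credible than an explanation offered after an inconclusive interval. Treating the unadjusted figure as conservative is also safe only if the follow-up SD is no larger than 0.8: at 0.9, unadjusted power with 80 analysable is 51.1%. The remedy would be cheap, namely one reworded paragraph and a small table, with no access to outcome data.

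Part of this stands. The SAP prints no power value, does not label its figures as unadjusted, and does not say why inclusion stopped at 100.

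The rest does not carry a change. Sizing on the raw SD and analysing with baseline adjustment is ordinary practice. SAP 5.1 lists its inputs, and because none is a correlation or residual SD, the calculation is visibly unadjusted. The ANCOVA table would rest on assumed values and span about 58% to 99%, so it would leave the question open. On the limit of 100, Protocol 6.5 already allows the Scientific Committee to decide on additional inclusions if dropouts significantly affect numbers, and Protocol 11.1's recalculation was carried out and reported. SAP section 6 concerns changes to analyses, and the protocol summary already permits an ANCOVA. The ANOVA in Protocol 11.2.4 is an inconsistency within the protocol about the model, separate from the sample size.

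**Conclusion.** No change to the plan is needed. The 63 per group, the 126 and the statement about power are correct for an unadjusted comparison with SD 0.8, and the shortfall against 80% is openly stated. What is missing is its size, which a statistician recovers in one line: about 70% with 100 analysable, 68–69% with 96, and 60–61% with 80. These figures assume that the 3-month SD equals the baseline 0.8; the last also assumes that 20% of the 100 are lost.

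For the planned ANCOVA, the documents cannot show the statement about power to be right or wrong. With SD 0.8 and 80 analysable it would cease to hold above r of about 0.60, and no value of r is given.

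Nothing that will be decided depends on the gap. Inclusion had ended, the ANCOVA is fixed, and non-inferiority turns on the confidence bound against 0.4. Once that interval is reported, its width gives the precision achieved more directly than any prospective power figure. Labelling the SAP 5.1 figures as unadjusted and explaining the limit of 100 would be a courtesy to the reader and would alter no result or conclusion.

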5.2 GENERALITIES FOR STATISTICAL ANALYSIS

Depending on the nature of the criteria studied, the descriptive statistics will be as follows: For categorical data: number of individuals, number of missing values, frequency and percentages of each of the variable's terms (excluding missing data in the denominator). Twosided 95% confidence intervals will be provided when deemed appropriate. Percentage will be presented to one decimal place.

Statistical analysis of quantitative data: number of individuals, number of missing values, mean, standard deviation, median, quartiles, minimum and maximum. The data will be presented as follows: 1 decimal place more than the original variable for mean and standard deviation, 0 for median, quartiles, min and max.

Statistical analyses will be performed using SAS® software, version 9.4, SAS Institute, NC, Cary, USA.

5.3 MISSING DATA MANAGEMENT

All incomplete study dates will be charged as follows:

- -The missing days will be replaced by 15
- -The missing months will be replaced by the month of June (06)

-Thus, if the day and month are missing, the date considered will be: 15/06/YYYY In case of calculation of duration resulting in negative values, these durations will be considered as missing.

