Study schedule	
Regulatory submissions (PPC): October 2019
 
Estimated date for obtaining all agreements: December 2019
 
Implementation of the centers: January to October 2020
 
Patient Recruitment: January to November 2020
 
Last patient visit: March 2021
 
Final base freeze: June 2021
 
Results on primary endpoint: September 2021
 
Validated clinical report: December 2021
 
Total duration of participation for each center = 7 months

ABBREVIATIONS

ANSM	National Agency for the Safety of Medicines and Health Products
ARC	Clinical Research Associate
ATC	Anatomical, Therapeutic and Chemical Classification
BPC	Good Clinical Practices (ISO 14155)
GMP	Good Manufacturing Practices
CNIL	National Commission for Information Technology and Civil Liberties
CNOM	National Council of the Order of Physicians
CPP	Committee for the Protection of Persons
CRO	Company Provider (Contract Research Organization)
eCRF	Electronic Case Report Form
EI	Undesirable Event
EIG	Serious Adverse Event
EIGI	Unexpected Serious Adverse Event
SD	Standard deviation
EVA	Visual Analog Scale
FAS	Full Analysis Set
HAS	High Authority for Health
HbA1c	Glycated Hemoglobin
ITT	Intent-to-treat
J	Day
M	Month
MEdDRA	Regulatory Medical Dictionary
NRS	Numerical scale score (0 to 10)
PP	Per Protocol
PT	Preferred Term
Q	Quartile
QoL	Quality of Life
RGPD	European General Data Protection Regulation (GDPR)
RIPH	Research Involving the Human Person
SOC	Organ System Classification
WHO	World Health Organization

CONTENTS

PROTOCOL VALIDATION PAGE	2
INVESTIGATOR SIGNATURE PAGE.....	5
SUMMARY OF THE PROTOCOL.....	6
ABBREVIATIONS	13
CONTENTS	14
1 INTRODUCTION	16
1.1 INTRODUCTION AND RATIONALE FOR THE STUDY.....	16
2 METHODOLOGY	18
2.1 STUDY DESIGN	18
2.2 RATIONALE FOR THE STUDY DESIGN	18
3 MEDICAL DEVICE.....	19
3.1 IDENTIFICATION AND DESCRIPTION OF THE MEDICAL DEVICE UNDER STUDY.....	19
3.1.1 Mechanism of action of an insulin pump.....	19
3.1.2 Medical Device Under Review: A7+ TouchCare Medtrum Insulin Patch Pump	19
3.1.3 Procedure for using the device.....	22
3.1.4 Possible adverse events related to the use of the device	22
3.1.5 Packaging and labelling.....	22
3.1.6 Preservation and storage	22
3.1.7 Device supply.....	23
3.1.8 Randomization.....	23
3.1.9 Dispensing of devices	23
3.1.10 Return of devices	23

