13.2 INVESTIGATOR'S RESPONSIBILITIES

13.2.1 Notification of adverse events (AEs)

Patients will be encouraged to report any DM-related incidents and DM-related tolerance incidents to the investigator.

At each assessment, the investigator will interview the patient to determine if any adverse events have occurred.

The physician will report in the eCRF all DM-related incidents and DM-related tolerance incidents observed or spontaneously reported by the patient throughout the study (as soon as the patient's signed consent to participate in the study is obtained).

AEs not related to the DM or not related to the procedure for implanting the DM will not be reported in the eCRF. However, physicians must report any adverse reaction suspected to be due to a drug or product by mail to the regional pharmacovigilance center (CRPV) on which they depend or on the website <http://solidarites-sante.gouv.fr/soins-et-maladies/signalement-sante-gouv-fr>.

DM-related incidents and DM-related tolerance incidents will be documented in detail in the observation book (eCRF). The following information should be filled in:

- Date and time of AR onset,
- Duration of AE (indicating the total duration of the AE or symptom or determining this duration from the start and end dates and times of the evolution),
- Intensity of AE (mild, moderate, severe),
- The causal relationship of the AR to the DM AND/OR to the procedure related to the DM,
- Any action taken with respect to the product under investigation and to address this AR,
- Evolution of the AR (e.g. complete resolution, persistence...),

The investigator should assess the intensity, severity and causality of all adverse events.

These should be followed up until the event is resolved.

Determination of duration:

If the total duration of the AR or symptom is not directly indicated, it will be calculated from its onset and end dates.

Intensity Assessment :

The investigator will specify the intensity of the AE according to the following classification: mild, moderate, severe taking into account the possible degrees of intensity of the event according to the following definitions:

Slight	
 ▪ Causes mild or transient discomfort, not requiring intervention or treatment. ▪ Does not limit or interfere with daily activities.
Moderate	
 ▪ Causes enough discomfort to limit or interfere with daily activities. ▪ May require treatment.

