16 SCHEDULE OF THE STUDY

The projected schedule for the study is as follows:

- Regulatory submissions: October 2019
- Obtaining regulatory approvals: December 2019
- Implementation of the study: January to October 2020
- Patient Inclusion: January 2020 to November 2020
- End of follow-up of the last patient: March 2021
- Database freeze: June 2021
- Full study report with follow-up: December 2021

However, the total duration of the study or the recruitment period may vary depending on regulatory deadlines and recruitment capacities.

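### SAP 5.3 sets every incomplete date to the 15th and to June without bounds, so in-study device events can be dated outside the patient's own follow-up and short durations deleted

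*SAP*

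**What the plan says.** SAP 5.3 opens with its scope: "All incomplete study dates will be charged as follows". It then gives three rules:

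- Day: "The missing days will be replaced by 15".
- Month: "The missing months will be replaced by the month of June (06".
- Both: "if the day and month are missing, the date considered will be: 15/06/YYYY".

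The only safeguard is "In case of calculation of duration resulting in negative values, these durations will be considered as missing". The section does not separate history dates from dates inside the study, and it sets no earliest or latest permissible date.

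In-study dates are collected. For each device-related event, Protocol 13.2.1 asks for "Date and time of AR onset", and for a duration that is either entered directly or worked out from start and end. SAP 7.5 plans an individual listing of adverse events that includes duration.

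The planned calendar in Protocol section 16 is "Patient Inclusion: January 2020 to November 2020", with the last patient's follow-up ending in March 2021. Each patient is followed for 12 weeks. Omnipod patients may then use the Medtrum pump for one further month (V3 to V4).

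**The concern.** A mid-year default is harmless for the date diabetes was discovered, because SAP 4.4.3 uses it in years. Inside a 12-week window it is not:

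- Take a patient included on 1 September 2020 whose event ended on 10 October and whose onset month is missing. Onset becomes 15 June, before inclusion. The computed duration is 117 days, longer than the 84-day follow-up. It is positive, so the safeguard does not act.
- An event in January 2021 with the month missing is dated 15 June 2021, after the planned end of the trial in March 2021.
- Where the rule yields a negative duration, the value is discarded although the imputation caused the contradiction. Short events suffer most.

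At stake is whether the dates and durations shown for device-related events are possible and unbiased, in a study where device tolerance and incidents are stated secondary endpoints.

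**Working it through.** The documents give no figure for the effect of this rule, so there is none to reproduce.

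**Inputs**
- Imputation rule: SAP 5.3.
- Inclusion: 1 January to 30 November 2020 (Protocol section 16, planned), 335 days. Uniform inclusion is my assumption; actual dates are not given.
- Follow-up: V1 = day 0, V3 = day 84, V4 = day 112 for Omnipod patients who take the extra month.
- Event day uniform over follow-up: my assumption.
- Month missing is read as day and month missing, with the year known.

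**Dates outside V1-V3.** Every inclusion day is combined with every event day 0 to 84: 335 × 85 = 28,475 pairs. The rule is applied to each.

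- Month missing: 12,849 before V1 (45.1%) and 8,401 after V3 (29.5%). Total 21,250 / 28,475 = 74.6%.
- Only the day missing: 1,401 before V1 (4.9%) and 1,155 after V3 (4.1%). Total 2,556 / 28,475 = 9.0%. About another 9% move between V1-V2 and V2-V3, which changes the pump in neither arm.

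**Sensitivity to the calendar**

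| Inclusion window (2020) | Month missing, outside 84 days | Month missing, outside 112 days | Only day missing, outside 84 days |
|---|---|---|---|
| Jan-Nov (planned) | 74.6% | 66.3% | 9.0% |
| 13 May-Nov (from the date of the protocol version the SAP cites) | 83.2% | 83.2% | 9.5% |
| Jun-Nov | 91.8% | 91.8% | 9.0% |
| Sep-Nov | 100% | 100% | 8.9% |
| Jan-Mar | 90.1% | 59.3% | 8.9% |
| 23 Mar-15 Jun | 0% | 0% | 7.5% |

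The last row is the one favourable case: for an 84-day follow-up, 15 June lies inside only if inclusion fell from 23 March (84 days earlier) to 15 June.

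**Deleted durations.** Let the onset month and the end date be known and the onset day missing, with duration = end − onset. An event with true onset on day d of the month and length L gets a negative duration when d + L < 15. With onset uniform over the 366 days of 2020:

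- L = 3: d ≤ 11, so 11 × 12 = 132 of 366 = 36%.
- L = 7: d ≤ 7, so 7 × 12 = 84 of 366 = 23%.
- L = 14: d < 1, never.

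The durations that survive therefore lean long. This does not depend on how events are assigned to a period.

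**Side of V3, only if period came from the date.** Omnipod patients taking the extra month, planned calendar:

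- Only the day missing: 4.1% of events up to V3 move after it, and 14.9% of V3-V4 events move to V3 or earlier.
- Month missing: 29.5% and 55.4%.

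**The case against.** A reader might infer that the rule credits events to the wrong pump in the planned tables, because V3-V4 in the Omnipod arm is spent on the Medtrum pump. The documents do not support that. SAP 7.4.2 frames periods by visits. Incidents are summarised per period as yes/no and number of occurrences, and tolerance (SAP 7.5) as yes/no and greatest intensity. Protocol 7.4 to 7.6 collects these at V2, V3 and V4. The derived indicator for any tolerance problem uses no date, and the template by system organ class counts events and patients. No section assigns a period from an onset date. The V3 figures are therefore conditional, and they concern only Omnipod patients who take the optional month.

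A reader might also infer that most incomplete dates are affected. That holds only when the month is missing, and only on the planned calendar. With the day alone missing it is about 9%.

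Three further points stand:

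- The derived variables built from dates in SAP 4.4.3 use inclusion, visit, birth and diabetes-discovery dates, never an event date.
- Duration appears only in a listing, and the site may enter it directly.
- Protocol 9.3 provides for queries, and SAP 5.4 for a review of inconsistent data before the freeze. Either may catch some impossible dates.

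These controls do not remove the problem. Neither contains a rule for dates, and SAP 5.3 as written has the programmer impute first and discard negative results afterwards.

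**Conclusion.** The point holds in limited form. The rule is stated, covers in-study dates and is unbounded. On the planned calendar with uniform inclusion and event timing, it would place about 75% of in-study dates without a month, and about 9% of those without a day only, outside V1-V3. For month-missing dates the figure runs from 0% to 100% across the inclusion windows tried; for day-missing dates it stays between 7.5% and 9.5%. The handling of negative durations loses short events selectively (about 36% of 3-day events and 23% of 7-day events under the stated conditions, and no 14-day events).

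The documented consequence is wrong or missing dates and durations in the adverse event listing. Misplacement around V3 remains a possibility for as long as the SAP does not say how period is assigned. The primary endpoint does not depend on these dates. The documents do not say how many in-study dates are incomplete, and there may be few. This is a minor correction, worth making because it is cheap.

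**What to change.** Replace the single rule in SAP 5.3 with two:

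- **Medical-history dates:** keep the 15th and June.
- **In-study dates:** impute within the overlap of the known month (if any) and the interval from the previous visit (or pump start) to the visit at which the event was reported. Never go before V1 or after the last contact. State one fixed point in the overlap, such as its midpoint. If the overlap is empty, query the date.

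Also state that period is assigned by the reporting visit, so that events first arising after V3 and reported at V4 stay in V3-V4. Apply the bounds before computing durations, and query any duration that is still negative before the freeze instead of setting it to missing.

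By construction, no imputed date then leaves follow-up or crosses V3. The cost is one SAP paragraph and a small programming change, with no new data.
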